#### 6.6. Visit Windows

Since data might be documented under a wrong label (as a wrong visit) within the EDC system, all data will be (re-)assigned to a visit according to the column *Intervals for analysis* in Table 9.

Furthermore, if a subject has multiple values for a parameter within a visit window, the “worst” value will be used for that visit window summary (see Appendix 12.3), for efficacy endpoints the closest to the scheduled visit will be used (if two have the same distance from the scheduled visit the later one will be used).

For the analysis of the open-label treatment phase, only data after the first dose of the open-label treatment phase until the end of the study will be included, except Baseline-OL values, which are based on data assessed prior to the first dose of the open-label treatment phase. A delayed performed Week 52 MRI assessment will be eligible as the Baseline-OL assessment if it has been done within 14 days after starting the open-label treatment phase. In addition, eye exams will be assigned to the double-blind treatment phase, if it was performed until the end of the Week 52 protocol-specified visit window.

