### 3.1.2. Open-Label Populations

The following subject populations will be evaluated and used for presentation and analysis of the open-label data:

**Intention-to-Treat Open-Label (ITT-OL) Population:** all randomized subjects who received at least one dose of study drug from the open-label treatment phase or continued off-treatment during the open-label treatment phase (e.g., TOTOS subjects from the double-blind treatment phase). Subjects are analyzed as randomized.

**Per Protocol Open-Label (PP-OL) Population:** all randomized subjects who received at least one dose of study drug from the open-label treatment phase and without any important protocol deviation during the open-label treatment phase. Subjects are analyzed as randomized.

**Safety Open-Label (Safety-OL) Population:** all subjects who received at least one dose of study drug from the open-label treatment phase. Subjects are analyzed as treated.

**Pharmacokinetic Open-Label (PK-OL) Population:** all subjects who were administered at least one dose of study drug from the open-label treatment phase and have a subsequent analyzable open-label treatment phase PK sample.

**v5-Populations:** If the above-mentioned populations (e.g., ITT, and PP) are restricted to subjects randomized under study protocol version 5.0 or higher, which are the primary efficacy analysis populations, the population names are: ITTv5-OL, and PPv5-OL.

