## **6. STATISTICAL ANALYSIS OF OPEN-LABEL TREATMENT PHASE**

### **6.1. Introduction**

The rationale of a delayed-start design is that, when the active drug has a purely symptomatic effect and has no effect on neuropathologic process, a delay in administration should have no lasting effect on subjects (null hypothesis). An effect that slows the progression of disease by modifying the underlying biological pathology, rather than only attenuating symptoms, would be evident if late starters fail to “catch up” to early starters. Demonstrating a disease-modifying effect would imply a sustained benefit of starting such drugs early. Throughout (that is, both the controlled and delayed-start phases), all subjects and study personnel on-site are blinded to each subject’s randomization to the early-start or late-start treatment group (HMTM treatment history).

Only subjects completing the 52-week double-blind treatment phase on- or off-treatment are eligible to enter the open-label treatment phase. This includes subjects, that have been randomized under a protocol version before version 5 and includes subjects who re-consented on a protocol version 5+ after the randomization and who completed the 52-week double-blind treatment phase. Subjects who have been off-treatment at Week 52 (TOTOS) stay off-treatment and do not receive any open-label treatment phase study drug.

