### **6.2. Open-Label Treatment Phase Definitions**

Based on the HMTM treatment history during the double-blind treatment phase “late” starters are defined as subjects originally randomized to control, and “early” starters are defined as subjects originally randomized to HMTM 16 mg/day or HMTM 8 mg/day. The last available assessment – for the scales: the last available (upscaled) value – prior to or on the same day of the start of the open-label treatment (Visit 7, Week 52) will serve as the Baseline assessment of the open-label treatment phase (Baseline-OL). A delayed performed Week 52 MRI assessment will be eligible for the Baseline-OL assessment if it has been done within 14 days after starting the open-label treatment phase.

The treatment group of subjects originally randomized to control will be labeled as “MTC 8 mg/week”.

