**Table 9 Evaluation Intervals of the Open-Label Treatment Phase**

Evaluation (scheduled day)	Protocol-Specified Interval	Intervals for Analysis		
		Safety assessments	ADAS-cog 13 , ADCS-ADL 23 , MRI	MMSE, CDR
Week 52 (365) a	351 to 379 [ $\pm 14$ ]	320 to 379	320 to 456	320 to 548
Open-Label Week 56 (394)	380 to 408 [ $\pm 14$ ]	380 to 470	-	-
Open-Label Week 78 (548)	534 to 562 [ $\pm 14$ ]	471 to 638	457 to 638	-
Open-Label Week 104 (730)	716 to 744 [ $\pm 14$ ]	$\geq 639$	$\geq 639$	$> 548$

a Baseline visit for open-label treatment phase

Sponsor:	TauRx Therapeutics Ltd.		
Protocol:	TRx-237-039		
Document Version No.:	3.0	Document Date:	07-JUN-2023

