#### 6.10. Secondary Efficacy Endpoint Analysis

The goal of the open-label phase is to demonstrate disease modification by comparing the ADAS-cog11 change from Baseline-OL at Week 104 between early and later starters using a non-inferiority margin. According to the study protocol the non-inferiority margin will be set to 2 units, based on the estimated treatment effect of  $5.2 \pm 1.3$  (mean  $\pm$  standard error) units from a pooled analysis of the studies TRx-237-005 / TRx-237-015.

This non-inferiority margin, and the thresholds mentioned in Section 6.11, have been selected based on the results of the two previous phase 3 studies TRx-237-005, and TRx-237-015. It was planned to change the non-inferiority margin to 50% of the observed 52 treatment effect, should the decline and treatment effect for this study, seen after topline and full analysis of the double-blind treatment phase, deviate strongly from the expectations based on the TRx-237-005/TRx-237-015 results. With the knowledge of the double-blind treatment phase results, the non-inferiority margin will be as selected, based on the two previous phase 3 studies TRx-237-005, and TRx-237-015.

Efficacy analyses will be conducted using the PPv5-OL population (see Section 3.1.2) with no imputation of missing values. Upscaling for the scales will be performed. The ITTv5-OL population will be analyzed as a supplementary analysis and will include only those subjects with at least one post-Baseline-OL value.

The key secondary endpoint is the Baseline-OL adjusted decline in ADAS-cog11 from Baseline-OL at Week 104. Repeated measures on this endpoint scheduled at Week 78, and Week 104 will be treated using a mixed effects model. Suppose  $\mu_{\text{early}}$  and  $\mu_{\text{late}}$  are the corresponding means of decline at Week 104 for the early and late starters, then the null and alternative hypothesis can be written as:

$$H_0: \mu_{\text{early}} - \mu_{\text{late}} \geq 2; \text{ versus}$$

Sponsor:	TauRx Therapeutics Ltd.		
Protocol:	TRx-237-039		
Document Version No.:	3.0	Document Date:	07-JUN-2023

$H_1: \mu_{\text{early}} - \mu_{\text{late}} < 2$ .

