treatment indicator and the interaction term between treatment and visit, the randomization stratification variables (see Section 2.6) as fixed factors, and the respective efficacy Baseline/Baseline-OL value as covariate; with an unstructured covariance matrix and the Kenward and Roger method of calculating the denominator degrees of freedom for the tests of fixed effects. One version of the line graph will include/present the visits from Baseline to Week 104, including Baseline as the covariate in the model, and a second version will include/present the visits from Baseline-OL to Week 104, including Baseline-OL as the covariate in the model. This will be repeated for the verified AD diagnosis subgroups MCI-AD and probable AD.

Based on the ITTv5-OL population, the following pairwise correlations will be analyzed by means of scatter plots with symbolized treatment groups, which include both the parametric Pearson correlation coefficient and the non-parametric Spearman's rank correlation coefficient and their corresponding p-values for each treatment group, along with the regression lines:

- (Changes from Baseline): MRI whole brain volume at Week 52 vs. ADAS-cog11 at Week 104
- (Changes from Baseline): MRI whole brain volume at Week 52 vs. ADCS-ADL23 at Week 104
- (Changes from Baseline): MRI whole brain volume at Week 52 vs. CDR-SOB at Week 104
- (Changes from Baseline): MRI whole brain volume at Week 52 vs. MMSE at Week 104

Based on the ITTv5 population, for ADAS-cog13, ADAS-cog11, ADCS-ADL23, and the two MRI parameters whole brain volume and temporoparietal lobe volume, the observed change from Baseline at Weeks 26, 52, 78, and 104 will be analyzed with a paired t-test, separately for the subjects originally randomized to HMTM 16 mg/day and subjects originally randomized to MTC 8 mg/week. Two-sample t-test comparisons between the treatment groups for the respective endpoints and each of the Weeks 26, 52, 78, and 104 will be presented as well. This will be repeated for the verified AD diagnosis subgroups MCI-AD and probable AD.

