#### 6.13.2. Adverse Events

Adverse events (AEs) will be coded using the MedDRA version 20.1 and are displayed in tables and listings using SOC and Preferred Term (PT).

TEAEs during the open-label treatment phase are defined as AEs with:

- Onset after first dose of study drug of the open-label treatment phase or
- Worsen in intensity after first dose of study drug of the open-label treatment phase or
- Worsen in treatment relationship after first dose of study drug of the open-label treatment phase.

The total number of subjects and the numbers stratified by MedDRA SOC and PT, along with the corresponding percentage, will be derived and summarized by the original randomized treatment group from the double-blind treatment phase (MTC 8 mg/week, HMTM 8 mg/day, HMTM 16 mg/day), the pooled HMTM group (HMTM 8 mg/day + HMTM 16 mg/day), and overall, for the following events:

- Any TEAE
- Any TEAE with an onset on the first day of the open-label treatment phase after the first dose of the open-label treatment phase, complemented by a subject data listing
- Any TEAE (categorized by severity)
- Any TEAEs assessed by the Investigator as related to treatment (i.e., related or possibly related)
- Any TEAEs severe in intensity and assessed by the Investigator as related to treatment (as defined above)

Sponsor:	TauRx Therapeutics Ltd.		
Protocol:	TRx-237-039		
Document Version No.:	3.0	Document Date:	07-JUN-2023

---

- Any TEAE that resulted in interruption or discontinuation of study drug (presented separately and combined)
- Any serious adverse event (SAE)
- Any serious adverse reaction (SAR), which are the SAEs judged to be possibly related or related to the study drug by the Investigator
- Malignancies other than non-melanoma skin cancers
- *TauRx AE Groupings:* Subsets of TEAEs (defined by PT), summarized per grouping and sub-grouping (see Section 5.12.2).
- The protocol-specified AEs of special interest (AESI), which are hemolytic anemia and lens discoloration. A list of all identified events will be provided to the Statistical Programming team.

In addition, separate summaries of AEs by MedDRA SOC and PT will be provided for:

- Post-treatment TEAEs (after the open-label treatment phase)

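### The open-label TEAE table for subjects who enter off-treatment is empty as defined, and SAP 6.6 read literally also bars their Week 78 and Week 104 scores

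*SAP*

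**What the plan says.** SAP 6.1 lets subjects who finish the 52 weeks off-treatment (the TOTOS group) go on into the open-label phase, but without drug: "Subjects who have been off-treatment at Week 52 (TOTOS) stay off-treatment and do not receive any open-label treatment phase study drug". SAP 3.1.2 includes them in ITT-OL, and so in ITTv5-OL if randomized under protocol version 5.0 or later. That population takes subjects who had an open-label dose "or continued off-treatment during the open-label treatment phase (e.g., TOTOS subjects from the double-blind treatment phase").

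Three rules then decide what is analyzed:

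- SAP 6.6, on open-label data: "only data after the first dose of the open-label treatment phase until the end of the study will be included". The only exception is the open-label baseline (Baseline-OL), which the same sentence also defines by the first open-label dose.
- SAP 6.10, on the supplementary ITTv5-OL analysis: it "will include only those subjects with at least one post-Baseline-OL value".
- SAP 6.13.2, on open-label TEAEs. The first branch reads "Onset after first dose of study drug of the open-label treatment phase or". The other two, worsening in intensity and worsening in treatment relationship, carry the same dose condition.

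SAP 6.13.2 goes on to order an any-TEAE table and an SAE listing for exactly the TOTOS subjects who continue off-treatment.

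Other text uses a visit instead of a dose. In SAP 6.2, the last value "prior to or on the same day of the start of the open-label treatment (Visit 7, Week 52) will serve as the Baseline assessment". The Table 9 footnote calls Week 52 the "Baseline visit for open-label treatment phase". SAP 1.6 includes all data to the end of the study in the open-label analysis.

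**The concern.** The SAP deliberately adds undosed subjects to a population and orders a safety table for them, then anchors the data rules to an event they never have. No sentence gives them a substitute start date.

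Two outputs are exposed. The TOTOS TEAE table cannot contain any event under its own definition. The ITTv5-OL analysis is the intention-to-treat check on a per-protocol delayed-start test, and it could be run with or without the off-treatment subjects depending on which sentence is followed. The safety table matters most for undosed control subjects. They are outside Safety-OL, and also outside Safety-HMTM because they never received HMTM. This is the only TEAE summary in SAP section 6 dedicated to their open-label events.

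**Working it through.** The plan states no figure on this point, so the check applies each rule in turn to a subject who is off-treatment at Week 52 and stays in the study to Week 104.

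**1. TEAE table.** The subject has no first open-label dose (SAP 6.1). Branches of the open-label definition that can be met: 0 of 3. The table is empty.

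The alternative is the general cross-reference from SAP 6.13.2 to 5.12.2, where an event counts from the first dose of any study drug. On the scheduled days in Tables 5 and 9:

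- period covered under 5.12.2: Day 1 to Day 730 = 730 days;
- part of it that is double-blind: Day 1 to Day 365 = 365 days, and 365 / 730 = 50%;
- period the table is meant to describe: 730 − 365 = 365 days.

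Neither definition yields a table of events during the open-label phase.

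**2. Efficacy visits.** Two post-baseline visits are scheduled, Weeks 78 and 104.

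- SAP 6.6 read literally: no value can fall after a dose that never occurs, so 0 of 2 visits are admitted. With no post-Baseline-OL value, SAP 6.10 removes the subject from the ITTv5-OL analysis.
- Table 9 study-day windows (Days 457 to 638, and Day 639 onward), with Week 52 as baseline: 2 of 2 visits are admitted and the subject stays in.

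SAP 1.6, 6.2 and Table 9 support the second result. SAP 6.6 is the more specific sentence on which data enter the open-label analysis, and nothing says it gives way.

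**3. Key secondary test.** SAP 6.10 runs it on PPv5-OL, and SAP 3.1.2 requires at least one open-label dose for PP-OL. Undosed subjects are out under either reading, so the test and its stated power do not change.

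**4. Size.** A shift in the ITTv5-OL early-versus-late difference would depend on how many undosed subjects each arm has and how their change from Week 52 differs from the rest. The documents give neither, so no figure is offered.

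**The case against.** The best case against is that the intent is clear on the efficacy side. SAP 1.5 ends the double-blind phase at the Week 52 visit. SAP 1.6 assigns efficacy data up to the last double-blind visit to that phase and includes all data to study end in the open-label analysis. Table 9 places visits by study day and needs no dose. A general sentence in a visit-window section should not empty an inclusion that SAP 3.1.2 makes expressly. Nor is SAP 6.6 applied without exception: in SAP 6.12, "One version of the line graph will include/present the visits from Baseline to Week 104, including Baseline as the covariate in the model". SAP 3.1.1 also requires a population tracker from the open-label data review meeting, so membership is not left to each programmer. Finally, the output shells are in a separate document and might define the TOTOS table.

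Most of this stands as evidence of intent, and inclusion is the more sensible reading. It does not repair the text. The tracker settles who is in a population, not which of their visits are admitted or when their TEAE period begins. None of the visit-based passages overrides SAP 6.6, and none supplies a TEAE start date. The shells are not in the documents and cannot be relied on.

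A reader might infer more: that the delayed-start conclusion is compromised, that the SAP means to discard these scores, or that adverse events are lost. The documents do not support these. The key secondary population excludes undosed subjects by design. Exclusion of their scores is only the literal result of one sentence that conflicts with others. All on-study events go into the AE listing under SAP 5.12.2, and SAP 6.13.2 orders a separate SAE listing for these subjects.

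**Conclusion.** Wrong as written, minor. The TEAE half is firm: the stated definition cannot be met by any subject in the table it is meant to fill, and the only other definition in reach covers both phases. The efficacy half is a conflict between rules, in which SAP 6.6 taken literally gives 0 of 2 post-baseline visits and the surrounding text gives 2 of 2.

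What is affected is one descriptive safety table, the supplementary ITTv5-OL analysis, and the ITTv5-OL summaries and graphs in SAP 6.12. The conclusion rests on SAP 6.1 holding in practice, that is, on subjects off-treatment at Week 52 receiving no open-label drug. If no such subject entered the open-label phase, the defect has no consequence.

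**What to change.** Add to SAP 6.6 and 6.13.2, for ITT-OL subjects with no open-label dose:

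- The open-label phase starts on the day after the last day of the Week 52 (Visit 7) visit, or the day after scheduled Day 365 if Visit 7 is missing.
- Baseline-OL is the value that Table 9 assigns to Week 52, or the last available earlier value if there is none.
- Values that Table 9 assigns to Weeks 78 and 104 are included as post-Baseline-OL values.
- The TOTOS TEAE table counts adverse events with onset or worsening from that start date. The SAP 5.12.2 definition does not apply to it.

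Baseline should come from the Table 9 window and not be limited to values on or before the visit date. The efficacy window for Week 52 runs to Day 456, and a Week 52 score taken late would otherwise be neither baseline nor Week 78.

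The cost is a few sentences in two sections and one derived date. No new data are needed, since SAP 6.7 already lists the Week 52 visit date for ITT-OL subjects. Dosed subjects and PPv5-OL are unaffected. SAP version 3.0 followed partial unblinding, so the change should be recorded, dated, in SAP section 10 as made after it.

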**Table 9 Evaluation Intervals of the Open-Label Treatment Phase**

Evaluation (scheduled day)	Protocol-Specified Interval	Intervals for Analysis		
		Safety assessments	ADAS-cog 13 , ADCS-ADL 23 , MRI	MMSE, CDR
Week 52 (365) a	351 to 379 [ $\pm 14$ ]	320 to 379	320 to 456	320 to 548
Open-Label Week 56 (394)	380 to 408 [ $\pm 14$ ]	380 to 470	-	-
Open-Label Week 78 (548)	534 to 562 [ $\pm 14$ ]	471 to 638	457 to 638	-
Open-Label Week 104 (730)	716 to 744 [ $\pm 14$ ]	$\geq 639$	$\geq 639$	$> 548$

a Baseline visit for open-label treatment phase

Sponsor:	TauRx Therapeutics Ltd.		
Protocol:	TRx-237-039		
Document Version No.:	3.0	Document Date:	07-JUN-2023

## 6.7. Subject Disposition

The subject by-visit listing will be updated with the open-label treatment phase visits.

Based on the ITT population, the subject data listing from the double-blind treatment phase will be updated and extended with the disposition information from the open-label treatment phase:

- Protocol version under which the subject has been randomized
- First and last dose dates of study drug intake (by treatment phase)
- Last date (by treatment phase)
- A flag for the completion, and a flag for the TOTOS (see Section 4.4) (by treatment phase)
- All reasons why the subject did not complete the study/treatment phase, and a flag for the primary reason
- For the TOTOS, the reason why the subject discontinued the study drug

Based on the ITT-OL population, a subject data listing will provide an overview of the open-label treatment phase populations (see Section 3.1.2) and will list the following events (sorted by subject, and date; one row for each event):

- Affiliation to the study open-label treatment phase populations (one column per study population)
- Date of Week 52 visit
- Protocol re-consents during the open-label treatment phase, with the protocol version and signing dates (one row for each re-consent)
- Date and primary reason of study discontinuation during the open-label treatment phase
- Date of study drug discontinuation during the open-label treatment phase, if study drug discontinuation is permanent and if the date is different from the date of study discontinuation
- Any date of COVID-19 infection (during double-blind or open-label treatment phase)
- Any date of COVID-19 vaccination (during double-blind or open-label treatment phase)
- Date of Week 104 visit

The corresponding listing from the double-blind treatment phase will also be updated with the following information:

- Protocol re-consents during the open-label treatment phase, with the protocol version and signing dates (one row for each re-consent)
- Date and primary reason of study discontinuation during the open-label treatment phase

Sponsor:	TauRx Therapeutics Ltd.		
Protocol:	TRx-237-039		
Document Version No.:	3.0	Document Date:	07-JUN-2023

---

- Date of study drug discontinuation during the open-label treatment phase, if study drug discontinuation is permanent and if the date is different from the date of study discontinuation
- Any date of COVID-19 infection (during double-blind or open-label treatment phase)
- Any date of COVID-19 vaccination (during double-blind or open-label treatment phase)
- Date of Week 104 visit

Information on the number of subjects in each analysis population of the open-label treatment phase, the number of subjects completing the open-label treatment phase / the study (subsets on and off treatment), the number of subjects discontinuing the study drug but continuing the study, the primary reason for discontinuation of study drug and study, and all reasons for discontinuation of study drug and study will be tabulated. This will be done by HMTM treatment history and overall, for the ITTv5-OL, ITT-OL, and PPv5-OL populations. Furthermore, based on the ITTv5-OL population, this will be tabulated by region.

